4.3.10. Overall Survival

OS is defined as the number of months elapsed between the date of the first dose of selpercatinib and the date of death (whatever the cause). Patients who are alive or lost to follow-up as of the data cutoff date will be right-censored. The censoring date will be determined from the date the

patient was last known to be alive. Based on these considerations, OS will be calculated as follows:

$$\text{OS (months)} = (\text{Death or Censoring Date} - \text{First Dose Date} + 1) / 30.4375$$

The duration of OS will be summarized descriptively using the Kaplan-Meier method with the 95% CI about the median calculated using Greenwood's formula. Median follow-up for OS will be estimated according to the reverse Kaplan-Meier estimate of potential follow-up (Schemper and Smith 1996).

4.3.11. Safety Analyses

4.3.11.1. General Considerations

This section describes the statistical methods to be used for analyses intended to demonstrate the safety and tolerability of selpercatinib.

Safety will be assessed based on the incidence and severity of all AEs and SAEs. Changes in clinical laboratory tests, vital signs, body weight, performance status, and 12-lead ECGs also will be assessed. These data presentations will be performed for the safety analysis set as specified in Section 2.

4.3.11.2. Adverse Events

Summary tables will be provided for all reported treatment-emergent AEs and treatment-emergent SAEs, defined respectively, as AEs and SAEs that started on or after the date of the first dose of selpercatinib (Study Day 1). For cases in which it is not possible to ascertain treatment-emergence, the event will be classified as treatment-emergent.

The reported AE term will be coded using version 21.0 of the MedDRA. The severity of each AE will be graded by the Investigator based on version 4.03 of the National Cancer Institute CTCAE. If a severity grading scale does not exist for an AE, the investigator will classify the severity as mild, moderate, severe, life-threatening/debilitating, or fatal based on the criteria described in study protocol. The causal relationship between the occurrence of an AE and study drug will be judged by the Investigator as "related" or "not related."

AEs will be summarized based on the number and percentage of patients experiencing events by MedDRA system organ class and preferred term. If a patient experiences repeated episodes of the same AE (as defined by the MedDRA system organ class and preferred term), the event with the highest reported severity grade and the strongest causal relationship to study drug will be used for purposes of the incidence tabulations.

Tabular summaries will be provided for treatment-emergent AEs and SAEs:

- all AEs
- by maximum severity grade
- by relationship to study drug
- AEs with action of study drug withheld or dosage modified

- AEs with action of study drug permanently discontinued
- SAEs

Narratives will be prepared for all patients who meet one or more of the following conditions:

- death while on treatment or within 28 days of the last dose irrespective of cause
- treatment-emergent SAEs
- AE with action taken of study drug permanently discontinued

4.3.11.3. Deaths

Death information is reported in the study exit case report form for all deaths. Incidences of deaths are to be reported, along with the primary cause of death in a summary table. All deaths including on-study death (deaths that occurred within 28 days of treatment discontinuation) will be presented in a patient listing, which will supplement the narratives and will include the primary cause of death, cumulative duration of treatment, and the number of days between the date of the last dose of study drug and death.

4.3.11.4. Laboratory Values

Blood samples for the following clinical laboratory tests were collected and analyzed for safety:

- Hematology: hemoglobin, hematocrit, platelet count, red blood cell count, and white blood cell count with differential (neutrophils, lymphocytes, monocytes, eosinophils, and basophils)
- Serum chemistries (non-fasting): ALT, AST, blood urea nitrogen, total cholesterol, creatinine, glucose, lactate dehydrogenase, total and direct bilirubin, total protein, sodium, potassium, calcium, chloride, bicarbonate, magnesium, phosphate, and urea
- Thyroid panel: thyroid-stimulating hormone, free triiodothyronine, and free thyroxine

Clinical laboratory samples were processed at the clinical site or at an affiliated local laboratory facility. For purposes of analysis and reporting, laboratory values will be standardized using International System of Units or clinically appropriate units. For laboratory values that are reported using a nonnumeric qualifier (for example, less than [$<$] signs or greater than [$>$] signs), the reported numeric value will be used for analysis without the qualifier.

4.4.8.4.1 Incidence of Laboratory Abnormalities

Whenever defined, laboratory values will be assigned toxicity grades based on version 4.03 of the CTCAE. For some laboratory tests, these criteria may include qualifying definitions (for example, clinical AE and/or requirement for concomitant medication) in addition to the specific laboratory value used for the definition of the toxicity grades. For such tests, the qualifying definitions will not be used for the assignment of toxicity grades. Generic normal ranges may be applied whenever the percentage of missing reference range is not negligible.

The “worst” change (minimum and/or maximum) in each laboratory value occurring during treatment will be assessed by means of shift tables showing the number and proportion of patients with directional shifts in CTCAE toxicity grades relative to the baseline grade. For laboratory variables without CTCAE toxicity grades (such as thyroid function), similar tables

will be constructed showing shifts to outside (above or below) the local laboratory normal range relative to baseline.

4.4.8.4.2 Changes in Laboratory Values from Baseline

Hematology, serum chemistry, and thyroid function values will be summarized in a descriptive manner by calculating the mean, standard deviation, median, and range of the following values that are derived for each patient:

- baseline value
- minimum postbaseline value and corresponding change from baseline
- maximum postbaseline value and corresponding change from baseline
- last postbaseline value and corresponding change from baseline

The baseline value will be determined using the convention described in Section 4.1.1. In addition, incidence of the most extreme treatment-emergent postbaseline abnormal laboratory parameters will be summarized. The treatment-emergent laboratory abnormality is defined as a laboratory value at least 1 toxicity grade higher than the baseline grade.

4.4. Exploratory Endpoint Analysis

4.4.1. Disease Control Rate

DCR will be calculated based on the proportion of patients with best overall response confirmed CR, PR, or SD. DCR will be measured from the date of the first dose selpercatinib until the criteria for disease progression are first met. The analysis of DCR will be based on the methods described for ORR and will be presented in the summary table of best overall response and ORR.

4.4.2. Intra-patient Analysis

Prior therapy data will be used to perform an exploratory analysis comparing benefit achieved on the last therapy patients received prior to the study enrollment to benefit achieved on selpercatinib treatment using each study patient as their own control. A known limitation of this analysis is retrospective prior therapy data collection based on patients' medical records without central review and confirmation based on RECIST criteria.

4.5. Other Safety Analyses

4.5.1. Vital Signs

The following vital signs were measured at screening and at periodic time points (including end of treatment and safety follow-up) following the initiation of selpercatinib:

- systolic and diastolic blood pressures (mm Hg)
- heart rate (beats per minute)
- respiration rate (breaths per minute)
- body temperature (degrees Celsius)

Each of these vital signs will be summarized in a descriptive manner by calculating the mean, standard deviation, median, and range of the following values that are derived for each patient:

- baseline value
- minimum postbaseline value and corresponding change from baseline
- maximum postbaseline value and corresponding change from baseline
- last postbaseline value and corresponding change from baseline

The baseline value will be determined using the convention described in Section 4.1.1.

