### 1.7.1 Known and Anticipated Risks

As of a clinical data cut-off (May 8, 2022) for this study (LOXO-RET-17001 [J2G-OX-JZJA]), the following AEs of special interest include:

- Dry mouth (48.7% total, 38.4% related)
- Hypertension (41.5% total; 28.7% related)
- AST increased (37.8% total; 28.8% related)
- ALT increased (36.2% total; 29.1% related)
- Electrocardiogram QT prolonged (20.5% total, 16.1% related)

Additional details on the safety profile of selpercatinib are provided in the selpercatinib IB.

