**Notes:**

- In patients with thyroid and other head and neck cancers, imaging of the relevant areas (e.g., neck, skull base) is required at baseline; other areas of scanning may differ depending on disease type. See the separate Imaging Manual that will be distributed to the sites for details.
- Additional scans can be performed as needed to evaluate potential sites of disease.
- Disease assessments will utilize RECIST 1.1 or RANO as appropriate to tumor type (refer to Section 7.8.1).
- Guidelines on the technical parameters of how scans should be performed will be provided in the Imaging Manual
- Concomitant, ongoing medications plus those administered within 14 days prior to the planned start of treatment.

## 7.2 Cycle 1

The procedures listed below will be performed at the indicated intervals. Observations, routine laboratory tests, and HRQoL assessments will be performed prior to selpercatinib dosing on that day unless otherwise indicated. Routine clinic visits and C1D1 evaluations performed within  $\pm 2$  days of the nominal visit day will not be considered protocol deviations, with the exception of ECGs and PK, which must be performed relative to the dose of selpercatinib on that day as indicated below.

Laboratory values on C1D1 pre-dose must meet the inclusion/exclusion criteria for treatment to proceed.

### Day 1

- Symptom-directed physical examination, weight, and ECOG or Lansky score.
- Vital signs.
- Resting 12-lead ECG: pre-dose (up to 4 hours pre-dose).
- Serum or urine pregnancy test for women of childbearing potential (surgically sterilized females or those who have not experienced menses for at least 2 years are not required to be tested).
- Hematology (as described in Section 7.1).
- Serum chemistries (as described in Section 7.1).
- Liver function tests (as described in Section 7.1).
- Calcitonin, CEA: for patients with MTC only. For each patient, all tests for calcitonin and CEA should be performed in the same laboratory to minimize intra-patient, lab-to-lab variability in their measurement.
- Thyroglobulin: for patients with non-MTC thyroid cancer only (unless not measurable due to presence of anti-thyroglobulin antibodies). For each patient, all tests for thyroglobulin should be performed in the same laboratory to minimize intra-patient, lab-to-lab variability in their measurement.

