All deaths, including on-study deaths, that occur within 28 days of treatment discontinuation will be reported in a patient listing, which will include the primary cause of death and the number of days between the date of the last dose of study drug and death. For patients undergoing LTFU, the duration of survival following the initiation of study drug will be summarized in a descriptive manner using the Kaplan-Meier method. A summary of the anticancer therapies received after discontinuation of study drug will be provided.

Hematology and serum chemistries will be summarized in a descriptive manner by calculating the mean, standard deviation, median, and range, as follows:

- Baseline value
- Minimum post-baseline value

- Maximum post-baseline value
- Average post-baseline value
- Last post-baseline value.

Laboratory values will be assigned toxicity grades when available using the NCI CTCAE, version 4.03. Directional shifts in laboratory toxicity grades (comparing baseline grade with worst post-baseline grade) will be analyzed using standard shift tables, presenting number and proportion of patients and their maximum grade shift. For analytes without a toxicity grading scale, the shift table will present directional shifts from baseline to above or below the laboratory standard normal range using the maximum increase and/or decrease observed throughout the course of treatment/observation.

All patients will have pre-treatment baseline vital signs and pre-dose measurements on D1 of each cycle. The results for each vital sign will be summarized in a descriptive manner by calculating the mean, standard deviation, median, and range by time point in the same manner described for laboratory values. For these analyses, the minimum, maximum, average, and last post-baseline value will be determined relative to the baseline vital sign measurements only. In addition, serial vital signs measurements will be obtained pre- and post-dose on the first day of each patient's selpercatinib treatment in conjunction with serial PK sampling. For each patient, the vital signs change from the pre-dose value will be summarized in a descriptive manner. The Wilcoxon signed rank test may be used to assist in the identification of any systematic changes.

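### SAP 4.5.1 drops the protocol's average and by-time-point vital-sign summaries and sets no on-treatment window, so no table shows the size or time course of the blood-pressure change on drug

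*SAP*

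**What the plan says.** **SAP 4.5.1 (Vital Signs)** says that readings were taken at screening and "at periodic time points (including end of treatment and safety follow-up) following the initiation of selpercatinib". For each sign it gives the mean, SD, median and range of four per-patient quantities: the baseline value, the minimum with its change, the "maximum postbaseline value and corresponding change from baseline", and the "last postbaseline value and corresponding change from baseline". It states no on-treatment restriction.

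**Protocol 8.5.2 (Safety Analyses)** says that vital signs will be "summarized in a descriptive manner by calculating the mean, standard deviation, median, and range by time point", and names the minimum, maximum, average and last postbaseline values. It adds a first-day analysis: "serial vital signs measurements will be obtained pre- and post-dose on the first day" of treatment, tied to serial PK sampling, with an optional Wilcoxon signed rank test.

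**SAP 4.7 (Changes to Protocol-Planned Analyses)** lists one change, that efficacy is analysed by indication rather than by cohort. It does not mention vital signs.

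**Protocol 7.6 and Table 7-1** place the Safety Follow-Up visit, with vital signs, 28 days (+7) after the final dose.

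**The concern.** Hypertension is among the most frequent events in Protocol 1.7.1 (41.5% from any cause, 28.7% related), and SAP 4.5.4 names it as an event of special interest. The measured blood pressures should show how large the rise is, when it appears and whether it persists. A maximum and a minimum cannot show this, because both drift outward as readings accumulate even when nothing has changed. A last value cannot show it when it mixes readings on treatment with readings taken a month after stopping. The study is single-arm, so no comparator has the same drift to set against it. The tumour-specific safety sets in SAP 2.1 may also differ in length of follow-up, and so in expected maximum.

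The other measured risks are treated more fully. SAP 4.5.4 gives liver tests shift tables, time-to-event plots and Hy's Law criteria. SAP 4.5.5 gives QTcF a categorical shift analysis. Blood pressure has no shift, threshold or time-course analysis.

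**Working it through.** The plan states no figure for these summaries, so there is nothing to reproduce. The check has four steps.

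**1. What was dropped.**

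| Vital-sign summary | Protocol 8.5.2 | SAP 4.5.1 |
|---|---|---|
| Baseline, minimum, maximum, last | yes | yes |
| Average postbaseline value | yes | no |
| By time point | yes | no |
| First-day pre-/post-dose change | yes | no |

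SAP 4.1.2.2 says how by-visit summaries are presented, but assigns none to vital signs.

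**2. How the maximum behaves with no drug effect.** Scheduled postbaseline readings, from Table 7-1 and Protocol 7.3, are C1D8 and C1D15 (2), Day 1 of C2 to C6 (5), C7, C9, C11 and C13 (4), then one every 12 weeks. That gives 4 by week 8, 8 by week 24, 11 by week 48, 15 by week 96 and 24 by week 208.

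For n independent normal readings around a patient's own mean, the expected excess of the maximum, in within-patient SDs, is

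E[max] = ∫ x · n · φ(x) · Φ(x)^(n−1) dx.

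A single baseline reading has the same expectation as the patient's mean, so this is also the expected change from baseline. The serial-correlation columns come from 100,000 simulated patients with first-order autoregressive readings. The last column multiplies the unrounded independent result by an **assumed** SD of 6 to 12 mmHg, which is not in the documents.

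| Readings (week) | Independent | Correlation 0.3 | Correlation 0.5 | mmHg, independent, SD 6–12 |
|---|---|---|---|---|
| 4 (8) | 1.03 SD | 0.92 | 0.82 | 6.2–12.4 |
| 8 (24) | 1.42 SD | 1.34 | 1.24 | 8.5–17.1 |
| 11 (48) | 1.59 SD | 1.51 | 1.42 | 9.5–19.0 |
| 15 (96) | 1.74 SD | 1.68 | 1.59 | 10.4–20.8 |
| 24 (208) | 1.95 SD | 1.90 | 1.83 | 11.7–23.4 |

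The minimum mirrors this downward. The per-patient average and the mean at a given visit have expected shift 0 at any number of readings. SAP 4.1.2.2 also lets unscheduled visits feed best- and worst-case values, so the count for a given patient can exceed the schedule.

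**3. How the last value behaves.** Protocol 6.3.2 equates about 5 half-lives with 2 to 3 days, so one half-life is 2/5 = 0.4 to 3/5 = 0.6 day. Day 28 after the final dose is then 28/0.6 ≈ 47 to 28/0.4 = 70 half-lives. An End of Treatment reading at its 7-day limit is already 7/0.6 ≈ 12 to 7/0.4 ≈ 18 half-lives out.

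If a share f of last readings is off drug and the effect has fully washed out, a true mean rise d appears as d × (1 − f). With an illustrative d = 10 mmHg, assumed values of f = 20%, 40%, 60% and 80% give 8, 6, 4 and 2 mmHg. The documents do not give f. For patients still on treatment at the cutoff, the last reading is on drug.

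**4. The first-day analysis.** Protocol 7.2 lists Day 1 vital signs once and sets the default that "Observations, routine laboratory tests, and HRQoL assessments will be performed prior to selpercatinib dosing on that day unless otherwise indicated". It places PK sampling on Day 8, not Day 1. The serial first-day readings assumed in Protocol 8.5.2 therefore do not appear in the schedule.

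**The case against.** Several objections are fair.

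- **Hypertension is reported elsewhere.** A reader might infer that the known hypertension effect will be misreported. The documents do not support that. SAP 4.3.11.2 tabulates events by preferred term, maximum grade, relationship and action taken, and the 41.5% is itself an adverse-event rate that SAP 4.5.1 does not touch. This objection stands in full.
- **The extremes come from the protocol.** Minimum, maximum and last are all in Protocol 8.5.2, are labelled as such, and are descriptive. This stands: the fault is the omission and the missing window, not the introduction of extremes.
- **The by-time-point wording is arguable.** The protocol ties it to the manner used for laboratory values, whose list has no visit-by-visit table. This stands in part, but the average is lost on either reading.
- **Changes may be described in the CSR.** SAP 4.1 allows this for changes that alter no principal feature, so silence in SAP 4.7 breaks no stated rule. That is true, but nothing shows that the omission was intended, and a choice explained after the data are seen is weaker than one stated beforehand.
- **The off-drug share is unknown.** It would be tempting to say that the last value is usually off drug. The documents give no basis for that.
- **Means by visit are not a pure drug effect.** Antihypertensives, interruptions, dose reductions and dropout all act on them. They nevertheless describe blood pressure as observed on treatment, which none of the retained summaries does.

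The missing window is not a general SAP convention. SAP 4.5.3 limits the worst performance score to treatment, and SAP 4.4.8.4.1 does the same for laboratory shifts.

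**Conclusion.** The point holds in limited form, and the SAP should be changed. SAP 4.5.1 leaves out the average and by-time-point summaries planned in Protocol 8.5.2, without listing this in SAP 4.7, and counts Safety Follow-Up readings with no on-treatment window. No planned table then gives the size or time course of the on-treatment blood-pressure change.

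The expected no-effect excess of the maximum, about 1.0 SD with 4 readings and 1.7 SD with 15, assumes independent normal readings. Serial correlation of 0.5 lowers these to 0.82 and 1.59 SD but does not remove the growth. Any mmHg figure rests on an assumed SD, and the 15-reading case requires about two years on treatment, which the documents do not describe as typical. The dilution of the last value is certain in direction for patients who stopped and attended Safety Follow-Up, if blood pressure returns towards baseline after washout. Its overall size cannot be stated.

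Laboratory values have the same unwindowed last value (SAP 4.4.8.4.2), but this matters less because toxicity-grade shift tables and treatment-emergent abnormality rates support them.

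**What to change.** 1. In SAP 4.5.1, restore the change from baseline by visit and the average postbaseline value with its change.
2. Restrict the average, minimum, maximum and last values to an on-treatment window defined from the last dose date. Visit names will not serve, because an End of Treatment reading can be several days after the last dose. Show Safety Follow-Up readings in a separate row.
3. Apply the same window to the laboratory last value in SAP 4.4.8.4.2.
4. List any remaining departure from Protocol 8.5.2 in SAP 4.7, with the reason.
5. Reconcile the first-day pre-/post-dose analysis in Protocol 8.5.2 with the schedule in Protocol 7.2 and Table 7-1.

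A count of patients with any reading above 140/90 mmHg is not proposed. It depends on the maximum, so it too rises with the number of readings, and Protocol 6.2.4 uses that figure as a management target rather than an analysis threshold.

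The cost is SAP wording and a few descriptive tables, plus a protocol clarification for item 5. The readings for items 1 to 3 are already collected, and there is no added patient burden.

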4.5.2. Body Weight

Body weight was measured at screening and at periodic time points following the initiation of selpercatinib. Changes in body weight will be summarized in a descriptive manner based on the conventions for postbaseline changes in laboratory values.

4.5.3. Performance Status

Performance status is graded according to either the ECOG, or Lansky scales depending upon the patient's age and tumor type. Data from the Lansky scales will be mapped to the ECOG performance scale (0–5) to maximize uniformity. Shift table analysis of baseline vs worst on-treatment score will be presented.

4.5.4. Adverse Events of Special Interest

Based upon information available to date and/or known class effects of this compound, several categories of AE have been designated to be of special interest. These include the following which are discussed below:

- liver injury
- hypersensitivity
- hypertension
- QT prolongation

The latest list of adverse events of special interest will be included in the program level safety analysis plan. As the understanding of the safety of selpercatinib increases, the list will be modified as needed.

Liver function tests will be presented using conventional summary statistics, toxicity shift table analysis, and by time-to-event plots. Possible drug-induced liver injury will be assessed as defined in FDA guidance (FDA 2009). Hy's Law cases of drug-induced liver injury have the following components:

- The drug causes hepatocellular injury as evidenced by an elevation of ALT or AST to 3-fold or greater of the ULN relative to control (or in this context to baseline levels).
- In addition to the transaminase increases, an associated (that is, concomitant) elevation of total serum bilirubin to 2-fold or greater of the ULN without initial findings of cholestasis (elevated alkaline phosphatase) was found.
- No other explanation can be found for the combination of increased transaminase(s) and total bilirubin, such as viral hepatitis, preexisting acute liver disease, or concomitant drug capable of causing the observed injury.

Narratives will be prepared for patients who meet all criteria for Hy's Law; these will include medical history, description of the event, action taken (including study drug action), and outcome.

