Upon resolution, for patients who received 160 mg BID, selpercatinib may be resumed at a reduced dose of 80 mg BID with weekly LFT monitoring. In the absence of recurrent LFT abnormalities, the dose of selpercatinib may be escalated sequentially to 120 mg BID after a minimum of 2 weeks at 80 mg BID, and again to 160 mg BID, and after a minimum of 4 weeks at 120 mg BID. Once the patient has been treated at a stable dose of selpercatinib for a minimum of 1 cycle without recurrent LFT abnormalities, the frequency of LFT monitoring may be decreased (e.g., additional midcycle evaluation for 2 cycles and then at the start of every cycle thereafter). For patients who experience  $\geq$  Grade 3 elevated LFTs on a different dose than 160 mg BID, the dose should be reduced by 2 dose levels with subsequent re-escalation and monitoring as noted above upon resolution. If the patient experiences  $\geq$  Grade 3 elevated LFTs at a dose of 40 mg BID, selpercatinib should be discontinued.

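### Patients who meet the Hy's Law laboratory thresholds but have a competing explanation get a narrative only through the SAE, discontinuation or death triggers, and no listing of concurrent elevations is planned

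*SAP*

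**What the plan says.** SAP 4.5.4 names liver injury among the adverse events of special interest and sets out three components of a Hy's Law case:

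1. Hepatocellular injury, shown by "elevation of ALT or AST to 3-fold or greater of the ULN relative to control", with a parenthesis that substitutes baseline levels for control in this single-arm setting.
2. A concomitant "elevation of total serum bilirubin to 2-fold or greater of the ULN without initial findings of cholestasis".
3. "No other explanation can be found for the combination of increased transaminase(s) and total bilirubin". Viral hepatitis, pre-existing acute liver disease and a causative concomitant drug are given as examples.

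The rule that follows is "Narratives will be prepared for patients who meet all criteria for Hy's Law". Each narrative is to cover medical history, the event, the action taken and the outcome.

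SAP 4.3.11.2 has a separate, general rule: "Narratives will be prepared for all patients who meet one or more of the following conditions". The conditions are "death while on treatment or within 28 days of the last dose irrespective of cause", a treatment-emergent SAE, and "AE with action taken of study drug permanently discontinued".

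For liver tests, SAP 4.5.4 also plans summary statistics, toxicity shift tables and time-to-event plots. It says that possible drug-induced liver injury will be assessed as in a cited FDA guidance.

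**The concern.** The third component is a causality judgement. Making it a condition for the narrative means that attribution is settled before the document that would normally set out the evidence for it. Patients whose laboratory values meet both thresholds, but for whom somebody has named another cause, fall outside the liver-specific rule. These are the cases in which a contribution from the drug is hardest to exclude, and a reader of the final report would want to see them and judge the attribution.

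Competing explanations are foreseeable in this population. Protocol 4.1 admits patients with documented liver involvement, and Protocol 6.2.4 calls prior checkpoint-inhibitor treatment a potential contributor to liver test abnormalities. Transaminase elevation is also common: Protocol 1.7.1 reports increased AST in 37.8% and increased ALT in 36.2% of patients. At stake is how completely potential liver-injury cases are documented, not any efficacy result.

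**Working it through.** The plan gives no figure to reproduce, so the check follows one type of patient through both narrative rules. The patient has ALT or AST at 3 × ULN or more, concurrent bilirubin at 2 × ULN or more, no initial cholestasis, and a competing explanation.

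**Step 1. Liver-specific rule (SAP 4.5.4).** Components 1 and 2 are met and component 3 is not. All three are required, so no narrative follows from this rule.

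**Step 2. General rule (SAP 4.3.11.2).** Any one condition is enough, and none depends on cause.

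| What happens to the patient | Narrative planned? |
|---|---|
| Dies on treatment or within 28 days of the last dose | Yes |
| Event reported as a treatment-emergent SAE | Yes |
| Event reported as an AE with study drug permanently discontinued | Yes |
| Event non-serious, drug held or reduced, no other trigger | No |
| Event recorded only as disease progression, no other trigger | No |

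**Step 3. Can the last two rows occur under this protocol?**

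- *Discontinuation.* Under Protocol 6.2.4, liver tests at Grade 3 or higher lead to holding the drug and looking for other causes. For patients who received 160 mg BID, once the abnormality resolves, "selpercatinib may be resumed at a reduced dose of 80 mg BID with weekly LFT monitoring". Re-escalation may follow. That section calls for discontinuation only when such an elevation occurs at 40 mg BID. The discontinuation trigger therefore need not fire.
- *Seriousness.* Protocol 9.4 leaves the important-medical-event category to judgement. Neither document makes the combined laboratory thresholds serious in themselves.
- *Progression.* Protocol 9.4 does not report progression as an AE or SAE. The opening of Protocol 9 also keeps SAEs caused by progression out of reporting unless the investigator thinks them possibly drug-related. A liver event attributed to hepatic progression can therefore pass by the SAE trigger. If treatment then stops for progression, there may be no AE record to carry the discontinuation trigger.
- *AE recording.* Under Protocol 9, a laboratory abnormality becomes an AE only if the investigator considers it clinically relevant.

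**Step 4. Do other planned outputs show these patients?** The laboratory sections under SAP 4.3.11.4 work test by test: worst-grade shifts, minimum, maximum and last values, and treatment-emergent abnormalities. A patient with a high ALT and a patient with a high bilirubin each appear in their own table. No table, plot or listing identifies a patient who has both at once. The liver outputs in SAP 4.5.4 do not specify one either.

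**Step 5. Baseline.** Protocol 4.1, criterion 10, compared with the SAP thresholds:

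| | Entry ceiling, no liver involvement | Entry ceiling, liver involvement | SAP threshold |
|---|---|---|---|
| ALT/AST | 2.5 × ULN | 5 × ULN | 3 × ULN |
| Total bilirubin | 1.5 × ULN | 3 × ULN | 2 × ULN |

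Because 5 > 3 and 3 > 2, a patient with liver involvement can enter with both thresholds already met. Without liver involvement, both ceilings lie below the thresholds (2.5 < 3 and 1.5 < 2). Any laboratory-based listing must therefore show baseline values.

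**Step 6. Size.** The documents give no count of patients who meet both thresholds, no share of these with a competing explanation, and no share without a general trigger. All three are needed. An assumed rate for the first would count all laboratory cases, not the missed ones.

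**The case against.** A reader might infer that every potential case with a competing explanation goes without a narrative, or that serious liver toxicity will be under-documented. The documents do not support either reading. SAP 4.3.11.2 plans narratives for reported SAEs, permanent discontinuations for an AE, and deaths in the window, whatever the cause. What remains is mainly non-serious events managed by interruption or reduction, plus events recorded as progression.

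Three further points have weight.

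- *The rule is not simply circular.* Protocol 6.2.4 already requires a search for other causes at Grade 3 or higher, including other hepatotoxic agents, viral serology and imaging. The exclusion judgement can therefore rest on a work-up done before any narrative. This stands. It makes the judgement better founded, but the final report would still not show the cases in which the judgement went the other way.
- *The likely alternatives are not shown to fail component 3.* Prior checkpoint inhibitors are called only a potential contributor, in some patients, and liver metastases are not among the SAP's examples. This stands as a limit on how often the gap arises. The examples are introduced as illustrations, however, so the list is not closed.
- *Other sources may fill the gap.* SAP 4.5.4 cites FDA guidance and a program-level safety analysis plan, and neither is available here. The SAP refers to the program-level plan for the current list of special-interest events, not for narrative rules. A general citation of guidance does not override an explicit rule on who gets a narrative. Handling of potential cases elsewhere in the program still cannot be ruled out.

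**Conclusion.** The point holds in a narrow form. The SAP's liver-specific narrative screens on attribution. A patient who meets the laboratory thresholds and has a competing explanation is narrated only if an SAE, permanent-discontinuation or death trigger also applies. No listing or count of concurrent elevations is planned to show the others.

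The number affected cannot be estimated from the documents and may be zero. No estimate, test or efficacy conclusion depends on it. The conclusion assumes that the SAP's wording is applied as written and that no document outside this set adds a laboratory-based trigger. This is an inexpensive improvement in liver-safety ascertainment, not the correction of an analysis error.

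**What to change.** Amend SAP 4.5.4 as follows:

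- Produce a listing, with a count, of all patients with post-baseline ALT or AST at 3 × ULN or more and concurrent total bilirubin at 2 × ULN or more, whatever the attribution. Define concurrent. The same sample date is workable, because the liver panel in Protocol Table 7-1 includes all these tests.
- Show alkaline phosphatase and baseline values in the listing, so that cholestasis and abnormal entry values are visible and not used as a screen. State how an elevated baseline is handled, since the reference to baseline levels in the first component leaves this unclear.
- Write a narrative for each listed patient and record the alternative-cause assessment inside it.
- Keep the full three-component definition for classifying confirmed Hy's Law cases.

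The cost is one listing and a small number of extra narratives, some of them in patients whose values were already raised at entry because of liver involvement. The laboratory data are already collected. No visit, efficacy analysis or clinical management rule changes.
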